6. TRIAL DESIGN

6.1. Study Endpoints

Primary endpoints, correlating to the primary objective of the study, will include determining the nature, frequency, and severity of AEs and/or SAEs associated with TDS-EP-based administration of HTNV, PUUV and HTNV/PUUV DNA vaccines.

- The occurrence of solicited local and systemic AEs occurring from the time of each injection through 14 days following the procedure
- The occurrence of vaccine-related unsolicited AEs from the time of the first injection through 28 days following each injection
- The occurrence of SAEs from the time of the first injection through the final study visit (approximately 6 months post-last vaccination)
- The occurrence of clinical safety laboratory AEs through 14 days following each study vaccination

Secondary endpoints, correlating to the secondary objectives of the study will be to determine the proportion of seropositive subjects ($\text{PsVNA50} \geq 1:20$) and the final overall rate of seroconversion over all scheduled time points to study completion for each study group. GMT will be calculated using PsVNA50 .

- Determination of the proportion of seropositive subjects (defined as $\text{PsVNA50} \geq 1:20$) at each scheduled time point (eg, Days 0, 28, 56, 84 and 140)
- Determination of the final overall rate of seroconversion over all scheduled time points to study completion for each study group. Seroconversion is defined as a post-vaccination HTNV- or PUUV-specific titer of $\geq 1:40$, or a minimum four-fold rise compared to baseline titer, and all study volunteers will begin the study with a baseline titer < 20 (ie, seronegative).
- Determination of GMT of the PsVNA50 for HTNV- and PUUV-specific neutralizing antibodies at each scheduled time point for each study group and over all time points for each study group.

Exploratory endpoints, evaluated as part of the immunogenicity objectives, including calculation of PsVNA80 titers for HTNV and PUUV may be calculated from the collected data for informational purposes, and neutralization assays using other hantavirus PsV (eg, Seoul virus, Dobrava virus) may also be performed to evaluate levels of cross-neutralizing antibodies.

- Determination of GMT of neutralizing of the PsVNA80 for HTNV- and PUUV-specific neutralizing antibodies at each scheduled time point for which blood samples are taken for each study group and over all time points for each study group

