8.1.3. Vaccination Visits

There will be 3 primary vaccination visits: Day 0, Day 28 ± 4 days, and Day 56 ± 4 days. Subjects will receive up to 3 vaccinations in the outer aspect of the subject's upper arm (deltoid area; alternating arms, beginning with left, if possible), using the TDS-IM V1.0 or TDS-ID EP system during the course of the study. Vaccine composition, vaccine dose and schedules (per group), subject randomization, and the TDS EP system have been discussed earlier in this protocol.

The following procedures will be performed during each vaccination visit:

- Review subject's medical history including concomitant medication use since screening or previous vaccination
- Review eligibility criteria with subjects and safety criteria including AEs, prior to study vaccination to ensure continued eligibility (see Section 7.5)
- Do a directed physical examination if indicated based on the subject's interim medical history (see also [Table 4](#)). Assess injection site prior to study vaccination to establish a baseline.

- Take resting vital sign measurement including oral temperature, heart rate, respiratory rate, and systolic and diastolic blood pressure. Subjects must not eat or drink anything hot or cold, or smoke within 10 minutes prior to taking oral temperature.
- Weigh subject, and if there is a $> 15\%$ change in body weight, measure skinfold thickness at potential injection sites with a caliper
- Perform a buccal swab for human leukocyte antigen (HLA) testing (Day 0 only)
- Collect approximately 22.5 mL of whole venous blood for the determination of:
 - CBC (WBC, Hb, platelets) with differential
 - Glucose, Cr, AST, ALT, total bilirubin
 - HTNV and PUUV-specific antibody as measured by PsVNA, using approximately 10 mL of the total 22.5 mL blood
- Urine sample collection for determination of pregnancy (must be negative prior to administration of the vaccine)
- Injection with study product
- Post-injection observation period/reactogenicity assessment (Subjects will be kept under observation for at least 30 minutes after each inoculation to ensure their safety, and any reactions during this period will be documented. Appropriate medical equipment and emergency medications, including epinephrine [1:1000], will be available on site in the event of an anaphylactic or other immediate allergic reaction.)
 - Give subject ruler and thermometer and explain how to use (Day 0 only)
 - Distribute memory aid and teach them how to complete memory aid

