8.1.4. Follow-Up Visits

There will be 9 follow-up visits: Day $2 + 1$ day, Day 14 ± 2 days, Day 30 ± 1 day, Day 42 ± 2 days, Day 58 ± 1 day, Day 70 ± 2 days, Day 84 ± 4 days and Day 140 ± 7 days and D220 Phone Call ± 14 days

The following procedures will be performed during each follow-up visit (some exceptions):

- Review of subject's medical history (including concomitant medications and AE) since previous visit
- Directed physical examination (injection site) if indicated based on the subject's interim medical history

- Take resting vital sign measurement including oral temperature, heart rate, respiratory rate, and systolic and diastolic blood pressure. Subjects must not eat or drink anything hot or cold, or smoke within 10 minutes prior to taking oral temperature.
- Review and collect memory aids (Days 14, 42, 70)
- Collect approximately 12.5 to 72.5 mL (depending on the scheduled visit day, see [Table 4](#)) of whole venous blood for the determination of:
 - CBC (WBC, Hb, platelets) with differential (Days 14, 42, and 70 only)
 - Glucose, Cr, AST, ALT, total bilirubin, (Days 14, 42, and 70)
- Collect blood for determination of HTNV- and PUUV-specific antibodies as measured by PsVNA assay (Days 84 and 140)
- Collect approximately 50 mL of blood for future research on Day 84 only
- Collect blood sample for determination of pregnancy test (Day 140 only)
- Perform ECG as last assessment of cardiac normality (Day 140 only)

Day 140 will be the final scheduled in-clinic visit for all subjects

Serious Adverse Event Final Telephone Follow Up Visit

There will be a scripted telephone follow up visit conducted at Day 220 ± 14 days.

- Review and collection of serious adverse events occurring since last visit conducted at Day 140.

Early Termination Visits

If a subject leaves the study early (see also Section [7.5](#)), procedures pertaining to Day 140 in the follow-up visit section (Section [8.1.4](#)) will be followed:

- Review of subject's medical history (including concomitant medications and AE) since previous visit
- Directed physical examination (injection site) and resting vital signs check (oral temperature (no recent hot or cold beverages or smoking), heart rate, respiratory rate, and systolic and diastolic blood pressure)
- Review and collection of any remaining memory aids
- HTNV- and PUUV-specific antibodies (PsVNA50 for final visit)
- Serum sample collection for determination of pregnancy test
- Perform ECG

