8.4. Subject Compliance and Memory Aid Completion

Subjects who are unable to follow the study requirements and arrive at study visits will be withdrawn from the study at the PI's discretion. Poor compliance with study visits would include the inability to come to a scheduled study visit within window on 2 or more occasions.

Withdrawal procedures for such instances are detailed in Section [7.5](#).

Following each injection, subjects will be provided a memory aid (ie, fillable diary card) and instructed in its use. On a daily basis during the 14-day period after each injection subjects will evaluate and record any local or general symptoms (eg, fever, myalgia, and malaise) they experience (see Section [10.3.2](#)). To more accurately account for possible fevers, subjects will be given an oral thermometer, instructed on its use, and asked to take and record their temperature daily for the first 14 days after each injection. Also, subjects will be asked to record local reactions at the injection site (such as erythema, edema, bruising, and pain) for 14 days after each injection. To more accurately account for the size of any such reactions, subjects will be given a ruler and instructed on how to use it. Memory aids will be reviewed by an investigator at follow-up visits during the 14-day post-injection period. Memory aids will be collected from the subjects at the 14-day post-injection visit. If memory aids are not completed or returned, an investigator will review the AEs that occurred during that time frame to the best of the subject's recollection. Subjects will be instructed on the use of the memory aid and encouraged to fill it out as directed; if it is not completed or not brought to a study visit by 28 days following each dose, then a protocol deviation will be documented. The maximum intensity reported by the subject whether recorded on the memory aid or verbally reported to the study staff will be recorded in the eCRF as an AE with a grade and relationship as determined by the assessing investigator.

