# expected scheduled visits						
# total scheduled visits						
# missed visits						
% scheduled visits completed						

TABLE 2.1: Injection Pain, Efficiency, and Speed by Treatment Group

^aIf more than one syringe was used, data from the last syringe is included in this table.

Q1: first quartile; Q3: third quartile.

TABLE 2.2: Global Summary of Adverse Events

Number of Participants Immunized= N	Possibly, Probably or Definitely Related Adverse Events	
	All Adverse Events	Events
Subjects with at least one solicited AE by 16 days of immunization [n (%)]	x (xx)	x (xx)
Total # solicited AEs [n (maximum severity grade)]	x (Grade X)	x (Grade X)
Subjects with a solicited Grade 3 AE [n (%)]	x (xx)	x (xx)
Subjects with at least one solicited local AE	x (xx)	x (xx)
Total # local AEs	x (Grade X)	x (Grade X)
Average # local AEs/volunteers experiencing local AEs	x.xx	x.xx
Subjects with at least one solicited systemic AE	x (xx)	x (xx)
Total # systemic AEs	x (Grade X)	x (Grade X)
Average # systemic AEs/volunteers experiencing systemic AEs	x.xx	x.xx
Subjects with at least one unsolicited AE within 32 days of immunization [n (%)]	x (xx)	x (xx)
Total # unsolicited AEs within 32 days of immunization [n (maximum severity grade)]	x (Grade X)	x (Grade X)
Subjects with an unsolicited Grade 3 AE [n (%)]	x (xx)	x (xx)
Subjects experiencing an SAE ^a [n (%)]	x (xx)	x (xx)
Total # of SAEs [n (maximum severity grade)]	x (Grade X)	x (Grade X)

a) An adverse event or suspected adverse reaction is considered “serious” (SAE) if, in the view of either the investigator or sponsor, it results in any of the following outcomes:

- Death
- Life-threatening adverse event
- Inpatient hospitalization or prolongation of existing hospitalization
- Persistent or significant incapacity or substantial disruption of the ability to conduct normal life functions
- Congenital anomaly/birth defect

TABLE 2.3.1: Number and Percentage of Subjects Experiencing Solicited Events by Symptom, Relationship to Study Product, and Treatment Group

NOTE: Table will be repeated for each injection dose

Symptom	Relationship to Study Product	Group 1 (N=X)		Group 2 (N=X)		Group 3 (N=X)		Group 4 (N=X)		Group 5 (N=X)		Group 6 (N=X)	
		n	%	n	%	n	%	n	%	n	%	n	%
Any Symptom	Related												
	Unrelated												
Redness, swelling, bruising, or pain (to include tenderness) at the injection site	Related												
	Unrelated												
Fever	Related												
	Unrelated												
Myalgia	Related												

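### Visits after doses 2 and 3 are tied to study day, not to the dose, so permitted visits can precede the injection or miss the 14-day safety window; SAP Table 2.2 uses other cut-offs

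*Protocol*

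**What the plan says.** **Dose timing.** Protocol 8.1.3: "There will be 3 primary vaccination visits: Day 0, Day 28 ± 4 days, and Day 56 ± 4 days". Dose 2 may therefore fall on Days 24-32 and dose 3 on Days 52-60.

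**Visit timing.** Protocol 8.1.4 lists the later visits as "Day 30 ± 1 day, Day 42 ± 2 days, Day 58 ± 1 day, Day 70 ± 2 days", and Table 4 has the same days and windows. Safety laboratory tests and diary collection after doses 2 and 3 are placed at the Day 42 and Day 70 visits. Neither section says that these days are recounted from the actual dose.

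**Endpoints.** Protocol 6.1 and 10.2 and SAP 3.3 count from the injection. The laboratory component is "The occurrence of clinical safety laboratory AEs through 14 days following each study vaccination". Solicited events also run to 14 days after each injection, and vaccine-related unsolicited events to 28 days.

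**Diary.** Protocol 8.4 has subjects record daily for 14 days after each injection and then says "Memory aids will be collected from the subjects at the 14-day post-injection visit". A deviation arises only if the diary is not completed or not brought in by 28 days after the dose.

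**SAP tables.** The Table 2.2 shell has rows for "Subjects with at least one solicited AE by 16 days of immunization" and "Subjects with at least one unsolicited AE within 32 days of immunization". SAP 8.5.3 limits the solicited analysis to 14 days. The SAP has no rule that assigns visits to windows relative to dose.

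**The concern.** Two clocks are in use. Endpoints run from the injection, but the visits that supply the scheduled measurements run from Day 0, with windows narrower than the dose window. A dose given early or late, but still within plan, changes the interval between injection and assessment. Protocol 7.4.1 makes late doses foreseeable, because a febrile illness or recent antibiotic use delays vaccination.

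The laboratory component of the primary objective is most exposed, because it depends on a single scheduled draw after each dose. The early visit matters too: several halting rules in Protocol 6.6 ask whether a Grade 3 event persists beyond 2 days, for any vaccination.

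Sites also face a conflict. A subject dosed on Day 32 and seen exactly 2 and 14 days later comes on Days 34 and 46. Both are outside the written windows (29-31 and 40-44). SAP Table 1.4 tabulates out-of-window visits as deviations, and Protocol 8.4 treats two or more missed windows as poor compliance.

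**Working it through.** **Inputs.** Dose days: 28 ± 4 and 56 ± 4 (Protocol 8.1.3). Early visits: 30 ± 1 and 58 ± 1. Two-week visits: 42 ± 2 and 70 ± 2 (Protocol 8.1.4, Table 4). Endpoint: 14 days after each vaccination (Protocol 6.1, 10.2).

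**Formula.** Offset = visit day − dose day.

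**Nominal timing reproduces the intended intervals.** 30 − 28 = 2 and 42 − 28 = 14; 58 − 56 = 2 and 70 − 56 = 14.

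**Extremes.** For dose 2, the early visit ranges from 29 − 32 = −3 to 31 − 24 = +7 days, and the two-week visit from 40 − 32 = +8 to 44 − 24 = +20 days. Dose 3 gives the same ranges: 57 − 60 = −3, 59 − 52 = +7, 68 − 60 = +8, 72 − 52 = +20.

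**By permitted dose day (days after dose):**

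| Dose 2 day | Dose 3 day | Early visit | Two-week visit |
|---|---|---|---|
| 24 | 52 | 5 to 7 | 16 to 20 |
| 25 | 53 | 4 to 6 | 15 to 19 |
| 26 | 54 | 3 to 5 | 14 to 18 |
| 27 | 55 | 2 to 4 | 13 to 17 |
| 28 | 56 | 1 to 3 | 12 to 16 |
| 29 | 57 | 0 to 2 | 11 to 15 |
| 30 | 58 | −1 to 1 | 10 to 14 |
| 31 | 59 | −2 to 0 | 9 to 13 |
| 32 | 60 | −3 to −1 | 8 to 12 |

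**Reading the table.**
- Early visit: on the last dose day (32 or 60) the whole visit window precedes the injection. On Day 31 or 59 no permitted visit falls after the dose day. Of the 9 × 3 = 27 whole-day pairs of dose day and visit day, 6 put the visit before the dose.
- Laboratory draw: on 2 of 9 dose days (24-25; 52-53) every permitted draw at the two-week visit is later than 14 days. No other scheduled draw fills the gap. After dose 2 the next is at the dose 3 visit, at least 52 − 25 = 27 days later. After Day 70 Table 4 has none. Of the 9 × 5 = 45 pairs, 20 are later than 14 days, 20 earlier and 5 exactly 14.
- Diary: on 2 of 9 dose days (31-32; 59-60) the collection visit always comes before 14 days, at 8 to 13 days.
- Even with an on-time dose, the draw may fall at 15 or 16 days. The same holds for dose 1 (Day 14 ± 2, so 12 to 16).

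**SAP cut-offs.** 16 − 14 = 2 days and 32 − 28 = 4 days longer than the SAP's own endpoints.

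**The case against.** The best reply is that dose-anchored visits were plainly intended. Protocol 8.4 describes the collection visit relative to the injection, Table 4 footnote e counts diary days from the vaccination visit, and visits are numbered in sequence, so Visit 5 follows the dose at Visit 4. In practice a site would probably see the subject after the dose and log an out-of-window visit. This stands as evidence of intent, but it conflicts with the study-day windows in Table 4 and 8.1.4, and the plan does not say which governs.

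A reader might infer that safety data would be lost. The documents do not support that:
- **Diary.** Entries run from the injection, return is allowed up to 28 days after the dose, and 8.4 has an investigator review events with the subject if the diary is missing or incomplete.
- **Early examination.** After Screen 1, physical examinations are complaint-driven (Table 4 footnote d). Reactogenicity is also captured by the observation of at least 30 minutes after injection, the diary and event assessment at every visit.
- **Laboratory results.** Nothing discards a draw at 15 to 20 days. SAP 8.5 and 8.8 summarise results by study day and collection point, and Protocol 10.6.1 collects adverse events to study end. A late result would be reported; it would only fall outside the endpoint as defined.

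On SAP Table 2.2, 16 = 14 + 2 and 32 = 28 + 4 match visit windows in Table 4, so these look like deliberate allowances. That is plausible, but it is unexplained and contradicts SAP 3.3 and 8.5.3. A reader might also expect Table 2.2 to disagree with Tables 2.3.1 and 2.3.2 for this reason. It would not agree directly in any case: Table 2.2 is global and the other two are repeated for each dose.

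**Conclusion.** The point holds as an internal inconsistency with a real effect inside the plan's own windows. The early visit can fall from −3 to +7 days and the two-week visit from +8 to +20 days around doses 2 and 3. On 2 of 9 permitted days for each of those doses, no scheduled post-dose draw can meet the 14-day laboratory endpoint. On 1 of 9, every permitted early visit precedes the injection. The diary limb is weak because 8.4 largely covers it. The SAP cut-offs are a separate contradiction of 2 and 4 days.

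This rests on reading the windows literally and in whole days. The counts show what is permitted, not how often it would happen; the documents give no distribution of dose days, and the worst cases need doses near the window edge.

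A reader might also conclude that the expected peak titer is compromised, since Day 84 ± 4 spans 80 − 60 = 20 to 88 − 52 = 36 days after dose 3. Protocol 4.4.2.1.1 says only that peaks in the earlier study generally came within a month of the last vaccination. It does not identify Day 84 as the peak, so that conclusion is not drawn here.

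**What to change.** 1. Reconcile Table 4 with Protocol 8.1.3, 8.1.4 and 8.4 so that the visits after doses 2 and 3 are counted from the actual dose date, with the sponsor setting the windows. For illustration, the existing ± 1 and ± 2 days would give offsets of 1 to 3 and 12 to 16 days, so no visit could precede its dose.
2. Because collection at 12 or 13 days would remain possible, state that a diary handed in before day 14 is completed and collected at the next contact.
3. State in Protocol 6.1 and 10.2 and SAP 3.3 that the laboratory endpoint includes the scheduled 14-day post-dose draw with its visit window, as well as any unscheduled result within 14 days. This settles draws at 15 or 16 days without excluding ad hoc tests.
4. Use one cut-off for solicited and one for unsolicited events throughout the SAP, by aligning Table 2.2 with SAP 3.3 and 8.5.3.
5. For subjects already completed, list actual days since dose. SAP Listing 1.7 gives actual study day, but Listing 1.10 gives dose dates only as counts by group, so the interval cannot be read for an individual.

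**Cost.** Amendment wording, SAP wording and table labels, and one derived listing variable; no added visits or blood. Calendar dates of later visits would shift with the dose date. Item 3 touches a primary endpoint after 36 subjects had been enrolled (Appendix B), so it should be recorded as a dated clarification. The same appendix shows 2 + 24 + 20 = 46 subjects still to enroll under Version 6.0, and Protocol 11 leaves the SAP open until database lock.

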4.5.1.4. Pregnancy

Risks to unborn babies are unknown at this time; pregnant females will be excluded from this study.

Sexually active men² and women³ of childbearing potential must be using an effective method of contraception from 30 days prior to the first study vaccination until 6 months after the last study vaccination.

All female subjects of childbearing potential must be abstinent or utilize effective contraceptive precautions. Non-childbearing potential is defined as either surgically sterilized or 1 year post-menopausal (defined as 12 consecutive months without menses). Study subjects should not become pregnant during the study and for at least 6 months after the last study vaccination.

Last, participants who are in non-male sexual relationships, abstaining from sexual intercourse with a male partner, or are in a monogamous sexual relationship with a vasectomized partner satisfy the study requirement to avoid pregnancy 30 days prior to the first study vaccination until 6 months after the last study vaccination (see inclusion criteria).

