7.3. Subject Inclusion Criteria

Subjects must meet all of the following criteria to be included in the study:

1. Healthy adult male or nonpregnant, nonlactating female, ages 18-49 (inclusive) at time of screening.
2. Have demonstrated adequate comprehension of the protocol by achieving a score of at least 80% correct on a short multiple-choice quiz. Individuals who fail to achieve a passing score on the initial quiz will be given the opportunity to retest after a review of protocol information. Individuals who fail the quiz for the second time will not be enrolled.
3. Have provided written informed consent before screening.
4. Free of clinically significant health problems, in the opinion of study investigators, as determined by pertinent medical history and clinical examination before entry into the study. (Refer to Synopsis for full description of terms).
5. Available and able to participate for all study visits and procedures.
6. Sexually active men⁶ and women of childbearing potential⁷ must agree to use an effective method of contraception from 30 days prior to the first study vaccination until 6 months after the last study vaccination.
7. Female subjects agree to not donate eggs (ova, oocytes), and male subjects agree to not donate sperm from the start of screening until at least 6 months after the last vaccination.
8. Female subjects of childbearing potential must have a negative serum pregnancy test at screening and a negative urine pregnancy test within 24 hours prior to each study vaccination.

⁶ A sexually active man is defined as one whose partner is a woman of childbearing potential (see definition below) and has not had a vasectomy performed > 1 year prior to screening. They must agree not to father a child until 6 months after the last vaccination. These subjects must agree to use a barrier method of birth control (eg, either condom with spermicidal foam/gel/film/cream or partner usage of occlusive cap [diaphragm or cervical/vault caps] with spermicidal foam/gel/film/cream/suppository).

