10.7.2.1. Pregnancy

Each pregnancy must be reported immediately using the Pregnancy Report Form (**within 24 hours of identification**) by e-mail or fax to the USAMRDC ORA PSSO. Report the incident to UMB IRB in accordance with IRB policy. USAMRDC ORA PSSO will be responsible for notifying DMID within 48 hours of notification by site.

Subjects who become pregnant after Day 0 will be followed until 30 days after delivery to determine outcome, including spontaneous or voluntary termination, details of the birth, and the presence or absence of any birth defects, congenital abnormalities, or maternal and/or newborn complications. The following information will be gathered for outcome, date of delivery, health status of the mother and child including the child's gender, height and weight. Complications and or abnormalities should be reported including any premature terminations. While pregnancy is not per se an AE/SAE, the product of the pregnancy could potentially be an AE/SAE. A pregnancy is reported as an AE or SAE only when there is suspicion that the investigational product may have interfered with the effectiveness of contraception or there was a serious complication in the pregnancy including a spontaneous abortion, an elective termination for medical rationale, or the infant has a congenital anomaly/birth defect.

Follow-up information should be e-mailed to [contact], using the Pregnancy Report Form stating that this is a trimester update or final report to the previously reported Pregnancy Report and giving the date of the original report.

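### No pregnancy question or test is scheduled after Day 140, although contraception is required until 6 months after the last dose; partner pregnancy is not asked about at any visit

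*Protocol*

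**What the plan says.** Inclusion criterion 6 (Protocol 7.3) requires effective contraception "from 30 days prior to the first study vaccination until 6 months after the last study vaccination". Section 4.5.1.4 says that risks to unborn babies are unknown, and adds: "Study subjects should not become pregnant during the study and for at least 6 months after the last study vaccination".

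Pregnancy is tested in serum at screening, in urine before each dose (8.1.3), and in serum at Day 140 or at early termination (8.1.4). Appendix D also places the last serum test at Visit 11, Day 140, and has no later column. Day 140 is the final clinic visit.

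After that comes one scripted telephone contact at Day 220 ± 14 days. Section 8.1.4 titles it as a serious adverse event call and lists one task: "Review and collection of serious adverse events occurring since last visit conducted at Day 140". Table 4 footnote o describes it in the same terms.

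On what counts as an event, 10.7.2.1 says: "While pregnancy is not per se an AE/SAE, the product of the pregnancy could potentially be an AE/SAE". It asks for a report within 24 hours of identification, and: "Subjects who become pregnant after Day 0 will be followed until 30 days after delivery to determine outcome". Section 7.5.5 gives similar follow-up for women who become pregnant and for men who report a partner's pregnancy. SAP 8.7 repeats the reporting rule and adds no way of finding a pregnancy.

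**The concern.** The protocol sets a period in which pregnancy is to be avoided, and a duty to report and follow any pregnancy that begins after Day 0. For the last part of that period it schedules no step that would bring a pregnancy to light. The one remaining contact is described as covering serious adverse events, and an uncomplicated pregnancy is not one. For partners of male subjects no question is scheduled at any visit.

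At stake is outcome information on exposed pregnancies for a product whose fetal risk the protocol calls unknown. If a pregnancy is not identified by the last contact, follow-up to 30 days after delivery starts only if the subject comes forward. After study completion, investigators are not obliged to look for serious events in former subjects (10.6.2). No endpoint, planned analysis or halting rule depends on this.

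**Working it through.** **Inputs**
- Last dose: Day 56 ± 4 (Protocol 8.1.3).
- Last pregnancy test: Day 140 ± 7 (8.1.4, Appendix D).
- Final call: Day 220 ± 14 (8.1.4).
- Contraception period: 30 days before the first dose to 6 months after the last (7.3, item 6).
- Month length: 28 days in the notes to Table 4. Criterion 6 gives no convention, so a calendar month of 365.25/12 = 30.44 days is shown as the alternative.

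**The plan's own figure.** Section 6.2 describes Day 220 as 6 months after the final injection. (220 − 56)/28 = 164/28 = 5.86 months, which agrees approximately. On calendar months, 164/30.44 = 5.39.

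**End of the contraception period**
- 28-day months: 56 + 6 × 28 = Day 224.
- Calendar months: 56 + 182.6 = Day 238.6.

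**Share of the post-dose period after the last test**
- 28-day: (224 − 140)/168 = 84/168 = 50%.
- Calendar: (238.6 − 140)/182.6 = 98.6/182.6 = 54%.

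**Share of the whole contraception period, from Day −30**
- 28-day: 84/(224 + 30) = 84/254 = 33%.
- Calendar: 98.6/268.6 = 37%.

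**Effect of visit windows on the post-dose share.** The extremes are dose 3 at Day 52 with the test at Day 147, and dose 3 at Day 60 with the test at Day 133.
- 28-day: 73/168 = 43% to 95/168 = 57%.
- Calendar: 87.6/182.6 = 48% to 109.6/182.6 = 60%.

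**Distance from the call to the end of the period**
- Nominal call: 224 − 220 = 4 days before the end, or 238.6 − 220 = 18.6 days on calendar months.
- The call may fall anywhere from Day 206 to Day 234. On 28-day months a late call can come after Day 224. On calendar months even Day 234 comes before Day 238.6.

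**What a call about serious events could find.** A pregnancy conceived after Day 140 is at most 220 − 140 = 80 days along at the nominal call, so no birth outcome can be known. A serious complication before the call, such as a spontaneous abortion, is reportable as an AE or SAE under 10.7.2.1 and would come within its scope. An uncomplicated pregnancy would not.

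**The case against.** The strongest reply is that the call may not be limited to serious events. Section 8.1.4 counts it among the nine follow-up visits, and its general list, which allows some exceptions, includes an interval medical history with concomitant medications and adverse events. Table 4 marks medical history, concomitant medications, adverse events, reactogenicity and vital signs at Visit 12. Section 10.6.1 has adverse events assessed at all study visits. A medical history is an ordinary way for a pregnancy to surface. This stands as a conflict within the protocol, but none of these entries mentions pregnancy, and the text specific to the call is narrower. The script is not among the documents, so one cannot say that it omits pregnancy, only that the protocol does not call for the question.

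Table 4 as it reads in the PDF text also shows a serum pregnancy test and an ECG under Visit 12. This is not evidence of a later test. The visit is a telephone call with 0 mL of blood, the ECG footnote says Visit 11, and 8.1.4 and Appendix D place the test at Day 140. Columns may have shifted in conversion: the administration row reads as Visits 5 and 8, although the Day 28 and Day 56 doses fall at Visits 4 and 7.

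A reader might infer that late pregnancies would go unreported. The documents do not support that: 7.5.5 and 10.7.2.1 apply to any pregnancy that is identified or volunteered.

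Numbers are likely to be small. The protocol defines effective contraception as under 1% failure per year with consistent, correct use. If all 82 subjects were at risk at that rate (an assumption), 82 × 0.01 × 80/365 = 0.18 pregnancies would be expected from Day 140 to Day 220. Actual use could give more; the documents do not say how many subjects are at risk.

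**Conclusion.** The point holds as a gap in active ascertainment. After Day 140 the protocol schedules no pregnancy test and states no pregnancy question, and it states no partner-pregnancy question at any time. The gap covers 50% of the 6 months after the last dose on 28-day months and 54% on calendar months, with 43% to 60% across the visit windows and both conventions. A reader might take this as half of the whole contraception period; counted from Day −30 it is 33% to 37%.

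The conclusion rests on reading the call as 8.1.4 and footnote o describe it. If the general follow-up list governs instead, a medical history is taken, but pregnancy is still not a stated item. The duty to report and follow known pregnancies is intact. The change is worth making because it costs little, not because many missed cases are expected.

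**What to change.** In 8.1.4 and Table 4 footnote o, state that the Day 220 call collects serious adverse events since Day 140, any pregnancy in the subject since Day 140, and any partner pregnancy since Day 0. Record positive answers on the existing Pregnancy Report Form, so that 10.7.2.1 applies. The earlier start for partners is needed because no earlier visit asks about them.

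At the same time, reconcile the Visit 12 entries in Table 4 (medical history, vital signs, serum pregnancy test, ECG) with 8.1.4, footnote o and Appendix D.

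The cost is a question or two and a script revision, with no added visit or sample. The contraception requirement itself is unchanged. Two limits remain: the answers are self-reported, and at the nominal call the last 4 days (28-day months) or about 19 days (calendar) of the period stay uncovered. A reminder on the call of when the restriction ends should not be added unless the sponsor first states which month convention applies.
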